**Using fMRI-guided TMS to Increase Central
Executive Function in Older Adults
(MCI_Sub)**

NCT04176406

This document includes the study protocol and the statistical plan approved on March 1st 2020.

Study Protocol:

This experimental supplement is focused on applying TMS to a cortical network node in 30 patients diagnosed with MCI or found to be at risk for cognitive impairment (This cohort will be referred to as "MCI patients", but includes subjects with diagnosed MCI and subjects not currently diagnosed, but at risk for cognitive impairment as defined by criteria below). This blinded, sham-controlled trial will feature a mixed model 2 x 3 x 2 x 2 cross-over design, with rTMS Type (active, sham), Difficulty Level defined by accuracy (easy, medium, hard levels), Stimulation Location (Network, Activity target), and Group (healthy OAs, MCI) as factors. As such, this design reflects the fact that all subjects receive both active and sham rTMS applied to up to two different scalp locations during a WM task at up to three levels of difficulty. Study procedures are listed in **Table 3**. Thirty healthy OAs (age range: 55-80 years) and thirty MCIs (age range: 55-80 years) will participate. In the first session, which will take about 2 hours, participants will be consented and screened for the study, submit a saliva sample for genetic testing, determine TMS motor threshold, and then learn and practice the WM task. The next visit will involve a structural MRI and fMRI recorded from both groups while they perform the WM task. Cortical locations within the FPN (Network target) and DLPFC (Activity target) will be used as targets for rTMS will be chosen from an analysis of subject-specific fMRI activations from the WM task completed in this MRI Session. This session, which will last up to 3 hours, will be followed by up to four sessions of rTMS + MRI, each lasting about 3 hours. These rTMS+MRI sessions will begin ~1 week after the MRI Session, to allow for time to process the imaging data. rTMS+MRI sessions (involving active or sham rTMS and Network or Activity targets) will use coil locations and rTMS device intensities based on realistic head modeling the MRI will collect structural and resting state information.

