the individualized target region, based on the cortical site with the highest computed controllability (Network target) or parametric activity (Activity target), using a MagVenture stimulator. Neuronavigation (BrainSight, Rogue Research, Canada) and a robot (SmartMove, ANT, Netherlands) will be used to optimize the targeting. Brain atrophy could also reduce TMS effectiveness because it increases the distance between scalp and the cortex but this potential confound is addressed by adjusting TMS intensity using the E-field computation. In visits 3 to 6, participants will perform the Working Memory Task while active or electrical sham stimulation is delivered using an A/P Cool-B65 coil (MagVenture, Denmark). In a stimulation trial, twenty-five pulses of 5Hz rTMS will be delivered at 100% of the effective E-field. Sham rTMS will be administered with a sham coil equipped with shielding to block magnetic field output but retain the auditory and some of the tactile aspects of active stimulation. This method reproduces the somatosensory sensations as the magnetic field stimulates scalp muscles, and produces the same acoustic artifact than the active stimulation, without inducing current in the cortex⁵⁹.

DWI Structural Connectivity. *Whole-brain tractography.* As in our prior DWI tractography work, Dipy⁶⁰ will be used to generate connectomes representing structural connections between all cortical regions in the Harvard-Oxford Atlas. For structural connection matrices, network edges are defined by the number of tractography streamlines between all nodes of the target network.

Event-related fMRI analyses, functional connectivity and graph theory measures. The Frontoparietal network (FPN) is identified by standard atlas⁶¹, and will be validated with voxelwise independent component analysis (ICA). Task-related connectivity is measured using beta-series correlations²⁰, which estimates a time-series by examining region-by-region interactions that are modulated by task conditions. SMEs for activity and connectivity will be analyzed with a Group (healthy OAs vs. MCIs) x Targeting (Network-based vs. Traditional) x Stimulation (Active vs. Sham) ANOVA using SPM⁶². All matrices are evaluated for descriptive graph-theoretical properties (including degree and controllability) using the Brain Connectivity Toolbox.

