E-field Modeling. In order to determine the *intensity* of network-based targeting, we will use electric field (E-field) modeling. The BSEL lab has extensive experience with the creation of anatomically realistic E-field models of transcranial electric and magnetic stimulation in humans, which have been applied to healthy OA populations in ongoing NIH-funded projects by Co-I's [name] and [name] (U01-AG050618), using SimNIBS software⁶³. A detailed model of the TMS coil is combined with a detailed head model. Isotropic tissue conductivities are assigned to the various tissue compartments. Critically, this method will also include anisotropic conductivity in the white matter based on the DWI data. We will carry out E-field simulations over a range of coil orientations and tilts to predict maximal activation of the FPN. The target node (i.e., the node with the highest controllability, identified above) will be used as the center of a 3×3 grid for positioning the coil in simulations of the E-field corresponding to these 9 coil positions and 6 orientations (54 combinations). The simulation E-field maps will be extracted and correlated, voxel-to-voxel, with the fMRI activation and the simulation that yields the highest correlation is selected as the target coil position and orientation.

Statistical Plan:

Power analysis. Our labs have considerable experience with combining neurostimulation and neuroimaging. Through the parent award we have enrolled 85 individuals in multiday memory protocols and results from these data reflect the size of potential future TMS effects. Power calculations were therefore conducted in R software (R Development Core Team, 2016) using the repeated-measures ANOVA module. With N=80 subjects, in a mixed-effects design consisting of 4 repeated measurements per subject (2 groups x 2 TMS targeting [network-based, traditional targeting]), Cohen's $d = 0.9$ for each of the main effects, with interaction effects between 0.7-0.9, attaining an average power of 0.8 at an overall significance level of 5%.

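### The stated average power of 0.8 is for 80 subjects and a layout that counts group among the repeated measures; the trial plans 60 subjects, each measured under active/sham by target

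*Combined protocol and SAP*

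**What the plan says.** The Power analysis paragraph of the Statistical Plan sets out its calculation as "With N=80 subjects, in a mixed-effects design consisting of 4 repeated measurements per subject (2 groups x 2 TMS targeting", the two targeting levels being network-based and traditional. It takes Cohen's d = 0.9 for each main effect, "with interaction effects between 0.7-0.9, attaining an average power of 0.8 at an overall significance level of 5" per cent.

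The rest of the document describes a different layout:

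- **Sample size.** The opening Study Protocol paragraph says "Thirty healthy OAs (age range: 55-80 years) and thirty MCIs (age range: 55-80 years) will participate". The same paragraph gives the MCI cohort size a second time: "applying TMS to a cortical network node in 30 patients diagnosed with MCI or found to be at risk for cognitive impairment".
- **Within-subject conditions.** In that paragraph, "all subjects receive both active and sham rTMS applied to up to two different scalp locations", and there are up to four rTMS + MRI "sessions (involving active or sham rTMS and Network or Activity targets"). TMS methods agrees: "In visits 3 to 6, participants will perform the Working Memory Task while active or electrical sham stimulation is delivered".
- **Analysis.** The section on event-related fMRI analyses specifies a "Group (healthy OAs vs. MCIs) x Targeting (Network-based vs. Traditional) x Stimulation (Active vs. Sham) ANOVA".

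**The concern.** This paragraph is the only quantitative support for the sample size, and it differs from the trial in three ways.

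1. It uses 80 subjects where 60 are planned. No dropout allowance or other enrolment target accounts for the difference. The only other sample in the paragraph is the 85 people enrolled under the parent award.
2. It builds four repeated measures from two groups and two targeting methods. A subject belongs to one group only, so group cannot multiply the measures taken on that subject.
3. It does not name active versus sham, which is the central contrast of a sham-controlled trial and a factor in the planned ANOVA.

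The result is also given only as an average, over effects that are not listed. An average can look satisfactory while the weakest test, here the three-way interaction, has little power. A reader cannot tell which effects have 0.8.

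**Working it through.** **Inputs from the documents.** Power calculation: N=80, d=0.9 for main effects, 0.7 to 0.9 for interactions, overall 5%, average power 0.8. Planned sample: 30 + 30 = 60. Planned ANOVA: Group x Targeting x Stimulation, which has seven effects.

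**Assumptions, because the plan is silent.** Two-sided 5% for each effect; a scalar outcome; equal groups; a common within-subject correlation rho of 0, 0.5 or 0.7; Difficulty averaged over. Unless stated otherwise, d is in units of the SD of a single measurement.

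**Layout.** Two targeting levels within subject give 2 measures. Active/sham x two targets gives 2 x 2 = 4, which matches the up to four sessions at visits 3 to 6.

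**Formulas.** Power comes from the noncentral t with N − 2 degrees of freedom. The noncentrality is (d/SD) x sqrt(N) for within-subject contrasts and (d/SD) x sqrt(N/4) for contrasts between groups. With four measures per subject, the contrast SDs are:

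- Group: sqrt((1 + 3rho)/4)
- Stimulation, Target, Group x Stimulation, Group x Target: sqrt(1 − rho)
- Stimulation x Target and the three-way: 2 sqrt(1 − rho)

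**Attempt to reproduce 0.8 at the plan's own N=80 (interactions 0.7).**

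| Layout | rho 0 | rho 0.5 | rho 0.7 |
|---|---|---|---|
| Literal: 2 groups x 2 targeting, 3 effects, mean power | 0.863 | 0.956 | 0.990 |
| Planned ANOVA, 7 effects, mean power | 0.850 | 0.938 | 0.971 |

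These readings do not return 0.8, but others can (see the objection). The stated figure cannot be pinned down from its own inputs.

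**Planned ANOVA at N=60 (main effects 0.9, interactions 0.7).**

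| Effect | rho 0 | rho 0.5 | rho 0.7 |
|---|---|---|---|
| Group | 1.000 | 0.991 | 0.973 |
| Stimulation; Target (each) | 1.000 | 1.000 | 1.000 |
| Stimulation x Target; Group x Stimulation; Group x Target (each) | 0.760 | 0.965 | 0.998 |
| Three-way | 0.266 | 0.470 | 0.682 |
| Mean of seven | 0.792 | 0.908 | 0.950 |

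Worked example, three-way at rho 0.5: SD = 2 x sqrt(0.5) = 1.414; noncentrality = (0.7/1.414) x sqrt(60/4) = 1.917; power 0.470. If the group d of 0.9 is instead on the SD of the subject mean, its power is 0.929.

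**Sensitivity of the three-way test.**

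| Setting | rho 0 | rho 0.5 | rho 0.7 |
|---|---|---|---|
| N=60, 0.7 SD | 0.266 | 0.470 | 0.682 |
| N=60, 0.9 SD | 0.403 | 0.679 | 0.879 |
| N=80, 0.7 SD | 0.340 | 0.590 | 0.806 |
| N=80, 0.9 SD | 0.511 | 0.803 | 0.952 |

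A simulation of the three-way test at N=60 (20,000 runs) gave 0.267/0.470/0.681 at 0.7 SD and 0.401/0.686/0.877 at 0.9 SD. At rho 0.8 and 0.7 SD, power at N=60 is 0.846. If d is on the SD of the contrast itself, rho drops out: the three-way has 0.760 (d=0.7) to 0.929 (d=0.9) at N=60, and the seven-effect mean is 0.887 to 0.959.

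**Effect of N alone.** An effect with exactly 0.80 power at N=80 has noncentrality of about 1.96 + 0.84 = 2.80. At N=60 this becomes 2.80 x sqrt(60/80) = 2.42, a power of about 0.68.

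**Subjects treated at one location.** The protocol says up to two locations and does not say how many subjects will have both. Two assumed cases for the three-way at 0.7 SD, rho 0/0.5/0.7: with 48 completing both, 0.221/0.389/0.582; with 36, 0.175/0.303/0.461. On the contrast SD (d=0.7 to 0.9) they are 0.661 to 0.863 and 0.532 to 0.746.

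**The case against.** - **The alpha level.** The plan speaks of an overall 5%, which may mean 5% divided among the effects. With a Bonferroni split at N=80, the literal layout gives a mean of 0.804 (alpha/3, rho 0, interaction 0.7). The seven-effect ANOVA gives 0.813 (alpha/7, rho 0.3, interaction 0.7) or 0.792 (alpha/7, rho 0, interaction 0.8). This stands: 0.8 is attainable at N=80 under some readings, so failure to reproduce it is not evidence of a wrong calculation. It does not help at N=60, and splitting alpha lowers the three-way power further.
- **The layout may be only a wording fault.** If active/sham is implicit in the four measures, the count is right and the bracket merely lists factors of the mixed design. That is possible and the document does not settle it. Even so, the sentence attributes the four to the wrong factors, and the N mismatch is untouched.
- **The three-way test is not named as primary, and the study calls itself exploratory.** Both are true. But the plan offers a formal power figure and specifies an ANOVA containing that interaction, so the figure should describe that analysis.
- **Difficulty and outcome.** The design also has three Difficulty levels, and the ANOVA concerns fMRI activity and connectivity, to which a scalar calculation may not carry over. This is fair. The plan's own power sentence also omits Difficulty and names no outcome.

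**Conclusion.** The concern holds. The mismatch of 80 against 60 and the use of group to build the repeated measures can be read directly from the text and depend on no modelling assumption. The 0.8 is therefore not a figure for this trial, and no figure is given for 60.

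Underpowering is not shown. Main effects remain well powered at N=60, and the average can be close to or above 0.8. What remains open is the power of individual interactions. For the three-way it runs from low to adequate, depending mainly on the correlation and the scale of d; the drop from 80 to 60 explains only part of that range. All power values here rest on a scalar outcome, equal groups, an assumed common correlation and an unsplit two-sided 5%. The paragraph should be corrected, but the design need not change on this account.

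**What to change.** Replace the power sentence with a calculation at N=60 (30 per group), with Group between subjects and Stimulation x Target as four within-subject measures.

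- Report power separately for active versus sham, Stimulation x Target, Group x Target and the three-way interaction, not as an average.
- State the outcome powered, the within-subject correlation, the scale on which d is defined, sidedness, and whether the 5% is split across effects.
- Say how the three Difficulty levels enter, for example averaged over.
- State that subjects treated at one location supply active versus sham but no targeting contrast, and give power for targeting effects on the number expected to complete both locations.

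If 80 was intended, explain it and reconcile it with the 30 + 30 in the Study Protocol.

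The cost is one re-run calculation and a rewritten paragraph, with no extra subjects or procedures. The likely downside is a less favourable stated power for the three-way interaction.

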Analytical Rigor. In our analysis phase, we will ensure scientific rigor in the following ways. To address bias in ANOVAs due potential violation of the sphericity assumption in Studies 1 and 2, we will estimate sphericity and correct for this bias using a Greenhouse-Geisser correction. In order to ensure replicability in our findings, we will report analytical procedures according to the Committee on Best Practice in Data Analysis and Sharing (COBIDAS) report for fMRI data analysis. Finally, to ensure generalizability of our findings, we will perform a k-fold cross-validation on all fMRI data analyses. In k-fold cross-validation, the data is divided into k independent subsets. On each fold, one subset is held out as the test set, the others are used for training. Empirical studies suggest that choices of k in the range of 5 to 10, yield good results in practice.

Consideration of sex as a biological variable. We will fulfill this recent NIH mandate by including both sexes in the research and by including gender as a covariate of interest in all analyses. Because this is an exploratory study, we have no a priori predictions on how gender might influence the TMS-imaging results. Although we may be underpowered to observe sex differences, the outcome of this Administrative Supplement can be used to estimate effect sizes to adequately power gender differences in future larger-scale studies.

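### No age term or age matching is stated for the healthy-versus-MCI comparison, so an age gap between the groups could bias the Group main effect

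*Combined protocol and SAP*

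**What the plan says.** - **Who is compared.** The opening of the Study Protocol sets the two cohorts: "Thirty healthy OAs (age range: 55-80 years) and thirty MCIs (age range: 55-80 years) will participate". The design lists "Group (healthy OAs, MCI) as factors". Membership follows from diagnosis or risk status, so Group is an observed between-subject factor.
- **What is within-subject.** The same paragraph describes a cross-over in which "all subjects receive both active and sham rTMS applied to up to two different scalp locations".
- **The model.** The section on event-related fMRI analyses, functional connectivity and graph theory measures specifies a "Group (healthy OAs vs. MCIs) x Targeting (Network-based vs. Traditional) x Stimulation (Active vs. Sham) ANOVA using SPM". Age is not in it.
- **Covariates.** The section on sex as a biological variable commits to "including gender as a covariate of interest in all analyses". No other covariate is named.
- **Nearest text to an age control.** TMS methods notes that brain atrophy could weaken stimulation and says "this potential confound is addressed by adjusting TMS intensity using the E-field computation". That concerns the intensity delivered, not the comparison of groups.

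Age appears only as the range for each cohort. No age covariate, age-stratified recruitment, age matching or age sensitivity analysis is stated.

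**The concern.** Two non-randomised groups can both lie within a 25-year range and still differ in mean age by several years. Age is a plausible predictor of working-memory accuracy, BOLD activity and connectivity. Without an age term, whatever part of the outcome follows age is credited to Group in proportion to the gap.

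At stake is the reading of the Group main effect as an effect of cognitive status. Group x Stimulation, Group x Targeting and the three-way term share the problem only if age changes how subjects respond to stimulation or to the target. The other safeguards do not reach it. The Greenhouse-Geisser correction deals with sphericity, and a confounded group difference would reproduce across cross-validation folds.

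**Working it through.** The plan gives no figure on this point to reproduce. The power paragraph ("With N=80 subjects, in a mixed-effects design consisting of 4 repeated measurements per subject") does not mention age and is not used here.

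**Inputs from the documents:** 30 per group; ages 55-80; 5% significance level (sidedness not given, two-sided taken).

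**Inputs assumed:** age SD of 25/√12 = 7.22 years (ages uniform over the range); difference in mean age D of 2-6 years; age-outcome correlation r of 0.2-0.4; no true Group effect.

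**Step 1, bias.** If the outcome depends linearly on age with slope r/SD (in outcome SD units), a Group coefficient fitted without age is off by

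spurious d = r x D / 7.22.

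Low corner: 0.2 x 2 / 7.22 = 0.055. High corner: 0.4 x 6 / 7.22 = 0.333.

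**Step 2, error rate.** Two-sample t test, 58 degrees of freedom, noncentrality d x √(30/2) = 3.87d:

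| Gap (years) | r = 0.2 | r = 0.3 | r = 0.4 |
|---|---|---|---|
| 0 | 0 SD, 5.0% | 0 SD, 5.0% | 0 SD, 5.0% |
| 2 | 0.055 SD, 5.5% | 0.083 SD, 6.2% | 0.111 SD, 7.1% |
| 4 | 0.111 SD, 7.1% | 0.166 SD, 9.7% | 0.222 SD, 13.5% |
| 6 | 0.166 SD, 9.7% | 0.249 SD, 15.8% | 0.333 SD, 24.5% |

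**Step 3, sensitivity to the assumptions.** With an age SD of 5 years, the 4-year, r = 0.3 case becomes 0.24 SD and 15.0%. With SD 7.22 but r = 0.5 and a 6-year gap, it is 0.42 SD and about 35%.

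**Step 4, does adjustment work?** Simulation used 5,000 runs per scenario, gaps of 0-6 years, r = 0.3 and 0.5, and gender in both models. With age added, the mean Group bias was within 0.004 SD of zero and the rejection rate was 4.7-5.5% in every scenario. Without age, the 2-6 year gaps gave 5.9-35.7%.

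**Step 5, interactions.** Each subject's active-minus-sham difference removes any age effect common to both conditions. Group x Stimulation is therefore biased only by (slope of that difference on age) x D, which is zero when age acts additively. The same holds for Targeting. The documents give no basis for a value of that slope, so no size is computed.

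**Step 6, price of adjustment.** At a 6-year gap the standardised age difference is 6/7.22 = 0.83. The R² between age and Group is 0.83²/(0.83² + 4) = 0.147, the variance inflation is 1/(1 - 0.147) = 1.17, and the standard error rises by √1.17 - 1 = 8%. Age also removes r² = 4-16% of residual variance. Multiplying by √(1 - r²) leaves a net change of about +6% (r = 0.2), +3% (r = 0.3) or -1% (r = 0.4).

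**The case against.** - **Silence is not exclusion.** The gender sentence answers a funder's requirement on sex as a biological variable. It says gender is included, not that nothing else is. The Study Protocol also points to cohort criteria and a Table 3 that are not in the text available for this review, and a matching rule could sit there. This stands: a reader might infer that age has been deliberately kept out of every model, but the documents support only that none is stated. Only one ANOVA is specified.
- **The harm is conditional.** It needs both an age gap and an age-outcome association, and the documents give neither. This stands. The 25% figure is the extreme corner of assumed inputs. The SD is also an uneasy choice, because two groups uniform over 55-80 would have no gap at all.
- **The cross-over protects the stimulation contrasts.** This stands. A reader might infer that the active-versus-sham or target effects are confounded by age; they are not.
- **Partial mitigation.** Difficulty is defined by accuracy. If levels are set per subject, which is not explicit, part of an age difference in accuracy would be absorbed. The E-field adjustment deals with one route by which age could alter response. Neither controls age in a Group comparison of BOLD activity or connectivity.
- **The study is called exploratory.** That lowers the weight of a nominal error rate. It does not remove bias from an estimate.

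**Conclusion.** The point holds as a gap in prespecification that is worth closing. It is not a demonstrated bias. A non-randomised Group comparison is planned with no stated age adjustment or matching, and a common age range does not supply either.

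On the assumed inputs (age SD 7.2 years, gap 2-6 years, correlation 0.2-0.4), the Group main effect would be off by 0.06-0.33 SD. A nominal 5% test at 30 versus 30 would reject about 6-25% of the time, with about 10% at a 4-year gap and a correlation of 0.3. With no gap it stays at 5%.

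It would go too far to say that the Group results are confounded, or that all Group interactions are. The first depends on an age gap and an age-outcome association that the documents do not report. The second depends further on age modifying the response to stimulation or targeting.

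**What to change.** - Prespecify centred age beside gender in every analysis that tests Group.
- Where a Group interaction is tested, add the matching age term: Age x Stimulation, Age x Targeting, and Age x Targeting x Stimulation for the three-way term. An age main effect alone does not protect the interactions.
- Name the age-adjusted Group result as primary and the unadjusted one as a sensitivity analysis, so that there is no choice between them after the data are seen.
- Report the age distribution by group. If recruitment is already age-matched, say so and describe how.

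**Cost.** Age is needed for eligibility, so no new data are collected. Each term uses one degree of freedom. At a 6-year gap the Group standard error is up to about 8% larger before the gain from lower residual variance, which offsets some or all of it over the assumed correlations.
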